Aim 2. Evaluate the preliminary efficacy of ACTivate in improving physical function and other outcomes in HCT patients (NIH Stage IB). As standard of care, all HCT patients undergo comprehensive functional evaluation (physical, cognitive, mental health, nutrition, social/financial, global, and quality of life) between sign-off (~10 days before HCT) and year 3. This will allow us to compare outcomes in the nine patients in Aim 1 plus an expansion cohort of 11 patients receiving the final iteration of ACTivate (total n=20) to contemporaneous controls matched for age, gender, and disease.

H1: Patients receiving ACTivate will have a shorter hospital stay and better physical function (six-minute walk, primary endpoint) at year 3.

3. **Background and Significance**

Allogeneic hematopoietic stem cell transplant (HCT) has the potential to cure patients with hematologic malignancies and other diseases, but treatment is arduous and there is significant risk of treatment-related morbidity and mortality. Worse clinical outcomes are predicted not only by advanced chronological age, but also by modifiable behavioral factors such as decreased physical function and comorbid psychological conditions, such as depression. Targeted interventions to reduce physical and psychological vulnerabilities during the pre-HCT time period could therefore improve treatment tolerance and HCT outcomes.

ACT [1] is a transdiagnostic, mindfulness-based treatment that has been effective in reducing psychological distress and symptom interference in a variety of clinical populations [2-5], including individuals with cancer [6-15]. Unlike more traditional cognitive-behavioral therapy (CBT), which focuses on changing thoughts/feelings themselves, ACT emphasizes psychological acceptance: voluntarily adopting an open, receptive posture with respect to moment-to-moment experience. This may be well-matched to individuals with cancer for whom distressing thoughts/feelings may not be illogical or irrational, but rather perfectly normal or expected responses to having a life-threatening illness (and embarking on a journey that could cure their disease but could also cause death), or simply inevitable during the course of treatment.

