Table 1. Assessments	Baseline	Every 2 Weeks	Continuous from Baseline	Day 30, Day 90, Day 180, Year 1, Year 2, Year 3
Physical function				
6-minute walk	X			X
Short physical performance battery	X			X
30 second sit-stand	X			X

Protocol Summary of: Pro00105683

Step count (activity tracker data)			X	
Falls question	X			X
PROMIS Fatigue*	X			X
PROMIS Physical Function*	X			X
Cognitive function				
Montreal Cognitive Assessment	X			X
PROMIS Cognitive Function*	X			X
Emotional / Psychological				
PHQ-9 (Depression)**	X			X
Valuing Questionnaire (VQ)*	X	X		
PC-PTSD/PCL**	X			X
PROMIS Depression**	X			X
PROMIS Anxiety**	X			X
PROMIS Emotional Support**	X			X
PROMIS Social Isolation**	X			X
HHI-12*	X			X
Brief COPE*	X			X
AAQ-II*	X			X
Nutrition				
Albumin	X			X
Body-mass index			X	
PONS	X			X
Clinician SGA	X			X
PG-SGA*	X			X
ASA-24*	X			X
Social/financial				
CMS Social determinants of health	X			X
FACIT-COST	X			X
Sociodemographics**	X			
SES (caregiver only)*	X			X (only Day 180, year 1, 2, 3)
Financial Assessment	X			X
Global				
Fried Frailty	X			X
OARS IADLs	X			X
Quality of life				
FACT BMT	X			X
FACT GP (caregiver only)*	X			X
EQ-5D-5L	X			X
Lorig Self Efficacy *	X			X
Self-Efficacy Preparedness for Caregivers (caregiver only)*	X			X
Miscellaneous				
PROMIS Global Health*	X			X

Protocol Summary of: Pro00105683

PROMIS Sleep*	X			X
HCT-CI (completed by MD)	X			
Clinical outcomes				
Adverse events (e.g., graft-host disease)			X	
Resource utilization (e.g., length of hospital stay)			X	
Symptoms				
PRO-CTCAE core symptoms*	Weekly through year 1			
Sample collections				
Stool**	X			X + Day 0, 7, 14, 21, 60
Skin**	X			X
Blood*	X			X + Day 14
Treatment development				
Acceptability survey**	X			X (only during ACT session time points as listed above)
Exit Interviews**				X
Note: Measures not collected as part of routine care are marked with an *. Measures marked with ** are assessments taken by caregivers too. All year 3 biosample collections will be optional.				

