Measures. Measures are outlined in Table 1. The majority of the assessments are collected as part of routine HCT procedures or tracked in the Duke Adult Bone Marrow Transplant (ABMT) database. Assessments that are not typically collected during HCT procedures have been marked with an (*). Primary outcomes will be the 6-minute walk and length of hospital stay. Target engagement (process of change) will be assessed with the Valuing Questionnaire (VQ) (or equivalent), administered to the patient and the caregiver every 2 weeks for the first 30 days, and once a month thereafter.

ACTivate sessions will be conducted in person or via the Duke extended care platform used for telehealth visits. Participants will also receive reminders of concepts from sessions and reinforcement or prompting from the study team via the custom HCT app (e.g., “Great job completing your steps yesterday!”). All sessions will be audio taped for fidelity review. Fidelity will be assessed with the ACT Measure (ACT-FM), along with an ACTivate protocol checklist (developed after finalization of the protocol in Aim 1). Session tapes from the second interventionist will be reviewed by [name] for ongoing training/consultation to maintain fidelity to the intervention.

Participants’ functional outcomes at Day 30 and Day 90 will be compared to age, gender, and disease-matched controls (case-control design), collected as standard of care.

Use of previously collected data: If a subject is simultaneously on another study and the same assessment or sample is required for both studies, we will only collect once and share the data between studies to avoid subjects having to duplicate efforts.

5. Selection of Subjects

Protocol Summary of: Pro00105683

Eligibility criteria: (1) Over the age of 18 (2) undergoing allogeneic HCT for any cancer or non-cancer illness, (3) English-speaking (4) has a caregiver who is willing to participate. Caregiver eligibility criteria: (1) Over the age of 18 and (2) English-speaking.

6. Subject Recruitment and Compensation

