Relationship of Risks to Benefits: This is a low risk intervention study that does not involve the use of a study drug or investigational device. No adverse health effects had been established from the use of the iPhone or Apple Watch. There is risk of loss of confidentiality, as with any study, and with studies with mobile devices. Treatment-related morbidity is high among HCT patients and mortality ranges from 10-30%. The potential benefit of interventions to increase treatment tolerance is thus substantial. Given the minimal risks associated with the study methods, the risk-benefit analysis is highly favorable.

10. Costs to the Subject

There are no direct costs to subjects.

11. Data Analysis & Statistical Considerations

Study variables will be described using summary statistics and graphical methods. Continuous variables (e.g., 6 minute walk (primary endpoint), AAQ2) will use the generalized linear model with the outcome of interest at year 3 as the dependent variable and treatment assignment as the primary predictor of interest, with a priori selected covariates age, gender, and disease. Ordered categorical outcomes (e.g. Fried Frailty) will use ordered logistic regression models in the same form above. Other outcomes (e.g., length of stay) will be assessed using an adaptation of the Cox regression model [35]. Primary analyses will be followed by examining the extent to which engagement is associated with outcomes using appropriate modeling. We also will explore the trajectory of outcome changes using generalized linear repeated measures models. We will carefully examine model assumptions (e.g., residuals, linearity, influential cases) and reparameterize models accordingly. Assuming an alpha of 0.05 and 10% attrition at 90 days, for the continuous outcomes, a sample size of 60 (20:40) will afford 80% power to detect a standardized group difference of just over 0.8 SDs. This translates to about a 16 meter treatment group difference in the six minute walk test.

12. Data & Safety monitoring

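### The primary six-minute-walk model uses one visit, omits baseline and earlier walks and states no missing-data method, so it gives up precision and would be biased if function-related loss differed between groups

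*Combined protocol and SAP*

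**What the plan says.** Section 11 specifies for continuous outcomes a "generalized linear model with the outcome of interest at year 3 as the dependent variable and treatment assignment as the primary predictor of interest". The only covariates, chosen in advance, are age, gender and disease. Neither the baseline walk nor any later walk before the analysis visit is a covariate. After the primary analyses comes the sentence "We also will explore the trajectory of outcome changes using generalized linear repeated measures models". No estimation method is named for those models. The protocol gives no analysis set, missing-data method, imputation or rule for deaths. The only attrition figure is 10% at 90 days, not split by group.

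Table 1 schedules the walk at baseline and again at "Day 30, Day 90, Day 180, Year 1, Year 2, Year 3", without the asterisk that marks measures outside routine care. Section 2 (Aim 2) says that "all HCT patients undergo comprehensive functional evaluation" as standard of care through year 3. Earlier walks should therefore exist for controls as well as for ACTivate patients.

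The analysis visit is not consistent. Section 2 hypothesises "better physical function (six-minute walk, primary endpoint) at year 3" and Section 11 agrees, but Section 4 (Measures) says that "functional outcomes at Day 30 and Day 90 will be compared to age, gender, and disease-matched controls".

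**The concern.** A regression on one visit's value, with nothing said about missing data, is fitted to the patients who have that value. A patient who walked at baseline, Day 30 and Day 180 but not at the analysis visit contributes nothing. If weaker living patients are more likely to miss the test, those who remain are fitter than the group they came from. When this selection is stronger in one group, part of the observed difference is selection.

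Unequal loss is plausible, though not documented. ACTivate patients have sessions, an app, a tracker and a caregiver acting as coach, while controls are followed only through routine care.

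The omitted baseline walk matters even with no loss. Controls are matched on age, gender and disease, not on function, and allocation is not random. The baseline walk is the obvious variable for adjusting a starting difference and reducing residual variance among 60 patients.

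**Working it through.** **1. The plan's own figure.** Inputs from Section 11: 60 patients (20:40), alpha 0.05 (two-sided assumed), 80% power, 10% attrition, leaving 18:36.
- Normal approximation: (1.960 + 0.842) × √(1/18 + 1/36) = 0.809 SD.
- Noncentral t: 0.824 SD.

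Both agree with the stated figure of just over 0.8 SD. The stated 16 m then implies an SD of about 16/0.8 = 20 m.

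**2. Bias of the single-visit difference.** The documents give no loss by group and no between-visit correlation, so these are assumptions: no true effect; earlier walk e standardised to mean 0 and SD 1; correlation r of 0.5 to 0.7 with the analysis-visit walk; and, among living patients, P(lost | e) = 1/(1 + exp(−(a − e))), with a set to give the chosen loss rate. The bias is r × (mean e among retained ACTivate patients − mean e among retained controls).

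| Loss, ACTivate / control | Mean e retained, ACTivate | Mean e retained, control | Bias, r = 0.5 | Bias, r = 0.7 |
|---|---|---|---|---|
| 13% / 29% | 0.116 | 0.245 | −0.064 SD (−1.3 m) | −0.090 SD (−1.8 m) |
| 8% / 12% | 0.074 | 0.108 | −0.017 SD (−0.3 m) | −0.024 SD (−0.5 m) |
| Equal rate, same dependence | equal | equal | 0 | 0 |

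Bias is also zero when loss is unequal but unrelated to e. A weaker dependence (0.7 rather than 1 on the logit scale per SD) gives −0.050 to −0.070 SD at 13%/29%. Stronger assumptions give more: −0.08 to −0.11 SD at 20%/40%, and up to −0.23 SD if, in addition, loss depends on function in controls only. The calculation ignores any part of e that age, gender and disease explain, which would shrink these figures.

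**3. Size against sampling error.** At 13%/29% about 17.4 and 28.4 patients remain. The standard error is √(1/17.4 + 1/28.4) = 0.304 SD, so the bias is 0.21 to 0.30 of a standard error. Two-sided type I error rises from 5% to about 5.5% to 6.0%.

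**4. The alternative.** A likelihood-type estimate that regresses on the earlier walk stayed within about 0.003 SD of zero in all simulated scenarios. This is expected, because loss was generated from that walk, so the data are missing at random by construction.

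**5. Precision from the baseline walk.** Adjustment multiplies the residual SD by about √(1 − r²): 0.87 at r = 0.5 and 0.71 at r = 0.7. Here r is the assumed baseline-to-outcome correlation after allowing for age, gender and disease. It could be lower at year 3, with a smaller gain.

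**The case against.** A reader might infer that the plan adopts a complete-case analysis and that its primary result is therefore biased. The documents do not support that. Complete-case handling follows by default from silence; it is not stated. Function-related loss is not enough for bias under no effect: the mechanism must also differ between groups. No loss by group is reported, and the walk is routine care for everyone, which weakens the case for unequal attendance. On the central assumptions the bias is small against the 16 m target. It also runs against ACTivate, so it would hide a benefit; heavier loss in ACTivate would reverse the sign. All of this stands.

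A reader might also blame the single-visit model for a detectable difference of 0.94 SD. That figure (noncentral t, 14:28) comes from assuming 30% loss in place of 10%, not from the choice of model.

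Two further objections limit the remedy. The plan's wording for its repeated-measures models also covers GEE, which unweighted does not generally protect against missing-at-random loss, so promoting that sentence as written would not suffice. With mortality given as 10-30%, some year 3 loss will be death, and a repeated-measures model does not settle what a walk after death means.

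The objections do not remove the absence of a missing-data method or the omission of a baseline walk already collected in both groups.

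**Conclusion.** The point holds as a conditional weakness and a worthwhile improvement, not as a demonstrated error in the result. Bias requires loss among living patients that depends on earlier function and differs between groups. Under the assumed 13%/29% loss and correlations of 0.5 to 0.7 it is about −0.06 to −0.09 SD (1.3 to 1.8 m). At losses nearer the 90-day attrition figure (8%/12%, assumed) it is about 0.02 SD, so which visit is primary largely decides how much it matters. The loss of precision and of control over baseline imbalance does not depend on any loss assumption, although its size depends on an assumed correlation. Since the data are already scheduled and a repeated-measures analysis is already contemplated, the change should be made before group results are seen.

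**What to change.** 1. Reconcile the primary visit: year 3 (Sections 2 and 11) or Day 30/Day 90 (Section 4, Measures).
2. Make the primary estimate the group contrast at that visit from a likelihood-based repeated-measures model, not unweighted GEE. Include group, visit, group-by-visit, baseline walk, age, gender and disease, with a simple covariance structure or fewer visits.
3. Keep the single-visit model, with baseline walk added, as a sensitivity analysis.
4. State that the model addresses missing walks in living patients under missing-at-random. Report missing walks and deaths separately by group, so that the estimate is not read as including walks after death.

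The cost is rewritten analysis text and an explicit statement on deaths; no new data are needed. The downside is that a covariance structure must be chosen with few patients.

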Significance. The curative potential of HCT is balanced by the significant risk of treatment-related morbidity, and mortality ranges from 10-30% [23-25]. Outcomes are worse in patients of advanced age, decreased physical function, and depressed mood [26-29]. Targeted interventions that reduce physical and psychological vulnerabilities pre-HCT have the potential to increase treatment tolerance and dramatically change illness trajectories and maintain long-term mobility and quality of life post-HCT, particularly for older adults. ACT is a newer CBT that has significant potential for this purpose [4]. ACT has decreased psychological distress and symptom interference and produced behavior change in a variety of clinical populations, including individuals with depression, anxiety, disordered eating, diabetes, and chronic pain [2-5]. Unlike traditional CBT, which focuses on correcting cognitive distortions, the target mechanism in ACT is psychological flexibility (the ability to allow experience to be what it is and move in the direction of values) [16]. Increased psychological flexibility may help HCT patients accept their situation (and the distressing thoughts/feelings that arise) and direct their attention to how they want to live the moments of their lives and to the things they can control.

For example, chemotherapy/radiation creates adverse interoceptive signaling (nausea, pain, fatigue) that may elicit maladaptive behavioral response patterns in HCT patients (sedentary behavior, disengagement, suboptimal nutritional intake). Individuals must actively choose to override these signals and engage in behaviors that may briefly intensify uncomfortable experiences in the service of improving treatment outcomes (walking, drinking protein shakes). Through ACT, individuals may better accept the discomfort associated with HCT and adapt behaviors in ways that improve function and survival. Further, the infusion of personal values in ACT may increase patient motivation to engage in health behaviors, even in the face of uncertain outcomes.

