In rare circumstances, and with the permission of the principle investigators, subjects may be allowed to use their personal activity tracking devices (such as an Apple Watch or FitBit) to track activity metrics such as step count. The activity tracking data from a subject's personal device will be shared with only key personnel on this study and with the subject's permission as outlined in the informed consent form. If subjects are allowed to use their personal activity tracker, we will only export activity data from their devices (such as a csv file) and will not be downloading the TRU-BMT or SplendoFit app on their personal device. Rare circumstances may include that subjects refuse to use the Duke provided Apple Watch and they have their own activity trackers.

Protocol Summary of: Pro00105683

Participants will complete informed consent procedures before the baseline assessment. Following the baseline assessment, patients and their caregivers will complete the first ACTivate session, and treatment will continue as outlined in Figure 2. ACTivate sessions will be audio recorded for training purposes to allow [name] to train others on how to conduct ACTivate sessions. Participants will be made aware that their sessions will be audio recorded at the time of informed consent procedures. Audio files will be recorded using a Duke encrypted Olympus DS Digital Voice Recorder on loan through the Duke Research Navigators program or using the Audacity software (Duke IRB approved) on an encrypted and password-protected Duke computer. The Olympus DS Digital Voice Recorder is password protected and has DSS Pro real-time 256-bit file encryption. Audio files will be saved to the project's secure folder behind the Duke server. Only IRB-approved key personnel will have access to the recorder and the audio recordings.

During Aim 1, we will make rapid iterations of the protocol after each cohort of $n=3$ to maximize acceptability and effectiveness (Stage 1A). All intervention will be conducted by [name] (a licensed psychologist with ACT expertise). For Aim 2, a second interventionist will be trained in the protocol, and we will continue to enroll patients in the final iteration of ACTivate until reaching 20 patients total (Stage 1B).

ACT Session Schedule

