Potential participants will be recruited from the Duke ABMT Program. Patients may learn about the study at the end of their new patient class, where the presenter will give the option for patients to stay after class and view a slideshow that briefly introduces the study. Under the current standard of care practice, ABMT physicians evaluate all new patients. If the patient's ABMT physician deems the patient to be an allogeneic transplant candidate and he/she meets basic eligibility criteria, the patient will be informed about the study. If the patient expresses interest in participating, they will be referred to research staff, who will review inclusion/exclusion criteria and tell the patient more about the study. Our target *N* is 20, and we anticipate achieving this target by recruiting 24 patients and caregivers. All recruited participants will be assigned to the intervention group, consistent with our use of a historical control group.

Participants will not receive direct compensation for participation in the study.

7. Consent Process

The ABMT physician and the research staff will make clear that participation in this research is voluntary, and patients may decline to hear more or to participate in the study without penalty; these patients will receive standard of care. Patients who are interested in learning more about the study will speak with study staff who will explain details, answer questions, and confirm inclusion/exclusion criteria. Caregivers will be identified by the HCT patient as a primary caregiver. They will be approached by study staff who will explain details, answer questions, and confirm inclusion/exclusion criteria. Patients and their caregivers will review the consent form with study staff in-person or over the phone. Potential participants will have ample time to ask questions and have those questions answered and consider whether they would like to participate. Only those who voluntarily provide full informed consent will proceed to study enrollment. Individuals who are screened but do not want to participate (do not give informed consent) will not be recorded and will receive standard care.

Subject's Capacity to Give Legally Effective Consent

We will exclude from participation anyone who does not have the capacity to give legal consent.

8. Study Interventions

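### The primary six-minute walk is at year 3, but the power statement allows only for 10% attrition at 90 days, so the stated 80% power is not shown for the primary analysis

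*Combined protocol and SAP*

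**What the plan says.** Three places set the time point of the primary comparison, and they disagree.

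- **Section 2, Aim 2, H1:** ACTivate patients are expected to have "better physical function (six-minute walk, primary endpoint) at year 3".
- **Section 11, model:** continuous outcomes, with the six-minute walk named as primary, use a "generalized linear model with the outcome of interest at year 3 as the dependent variable".
- **Section 11, power, same paragraph:** "Assuming an alpha of 0.05 and 10% attrition at 90 days, for the continuous outcomes, a sample size of 60 (20:40", which is said to give 80% power for just over 0.8 SD, or about 16 m.
- **Section 4, Measures:** "functional outcomes at Day 30 and Day 90 will be compared to age, gender, and disease-matched controls".

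Four other statements bear on the point:

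- Section 2 says that standard-of-care functional evaluation runs "between sign-off (~10 days before HCT) and year 3", and Table 1 schedules the six-minute walk through year 3.
- Section 3 says that "mortality ranges from 10-30" percent, with no time horizon. Section 9 repeats the range.
- Section 6 sets a target of 20 and says "we anticipate achieving this target by recruiting 24 patients and caregivers".
- Section 4 continues enrolment "until reaching 20 patients total".

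No year-3 attrition, evaluable number, SD or detectable difference appears anywhere.

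**The concern.** The 80% power and the 0.8 SD sit in the same paragraph as the year-3 model, so a reader will take them to describe the year-3 analysis. The loss allowance behind them belongs to Day 90. Loss accumulates between Day 90 and year 3, and a patient who has died has no year-3 walk. At the low end of the protocol's own mortality range, deaths alone would use up the 10% allowance if that range applies by year 3.

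Two things are at stake. If loss by year 3 is larger, the study can detect only a larger difference than stated, and a null year-3 result could be over-read. And with Day 90 in the control comparison and the power sentence but year 3 in the hypothesis and model, the text leaves room to choose the primary time point after data are seen.

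**Working it through.** **Inputs from Section 11:** alpha 0.05 (sidedness not stated), 20 ACTivate and 40 controls, 10% attrition, 80% power, just over 0.8 SD, about 16 m. **Assumed:** every loss fraction at year 3.

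**Method.** Two-sample comparison of means, two-sided alpha 0.05, noncentral t with df = n1 + n2 − 2 and noncentrality d / √(1/n1 + 1/n2). The detectable difference is the d that gives 80% power. The normal approximation is d = (1.960 + 0.842) × √(1/n1 + 1/n2).

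**Step 1: reproduce the plan's figure.**

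- No loss, 20:40: √(1/20 + 1/40) = 0.274. The normal approximation gives 0.77 SD and noncentral t gives 0.78 SD, both below 0.8.
- 10% loss, 18:36: √(1/18 + 1/36) = 0.289. The normal approximation gives 0.81 SD and noncentral t gives 0.82 SD, which matches the stated figure.
- A one-sided test at 18:36 would give about 87 to 88% power at 0.81 to 0.82 SD, so the plan's figure is two-sided.

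The stated result therefore depends on the 10% loss. The calculation uses the fraction and not the visit, so it holds at year 3 only if loss by year 3 is still about 10%.

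**Step 2: how much year-3 loss the stated figure tolerates.** With equal loss the limit is about 10% (18:36, 0.82 SD). With loss in ACTivate only it is about 15% (17:40, 0.83 SD).

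**Step 3: larger assumed losses at year 3.** Metres use the SD implied by the protocol, 16 / 0.82 = 19.5 m, assumed to hold at year 3 as well.

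| Assumed loss | Evaluable | Power at 0.82 SD | Detectable at 80% | Metres |
|---|---|---|---|---|
| 20%, both groups | 16:32 | 75% | 0.88 SD | 17.1 |
| 30%, both groups | 14:28 | 69% | 0.94 SD | 18.3 |
| 40%, both groups | 12:24 | 62% | 1.02 SD | 19.9 |
| 20%, ACTivate only | 16:40 | 78% | 0.84 SD | 16.5 |
| 30%, ACTivate only | 14:40 | 74% | 0.89 SD | 17.3 |
| 40%, ACTivate only | 12:40 | 69% | 0.94 SD | 18.3 |

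The ACTivate-only rows apply if the 40 controls are chosen because they have a year-3 walk. The documents do not say which case is meant.

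**Step 4: do the 24 recruits cover the gap?** The text does not say that all 24 are treated and followed. If they were:

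- 20% equal loss leaves 24 × 0.8 = 19.2, about 19, against 32: 0.83 SD, so the stated result survives.
- 30% ACTivate-only loss leaves 24 × 0.7 = 16.8, about 17, against 40: 0.83 SD, so it survives.
- 30% equal loss leaves 17:28: 0.88 SD and 74% power, so it does not.

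**The case against.** The strongest reply has five parts.

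1. **Year-3 control data have a source.** Section 2 says routine evaluation runs to year 3, and Section 4 does not say that Day 30 and Day 90 are the only comparisons or the primary ones. This stands: year-3 control values may well exist. But Section 4 still omits the comparison that H1 calls primary, and does not say how controls lost before year 3 are handled.
2. **The shortfall is assumed.** Every year-3 loss above is an assumption, and the mortality range has no horizon. At 20% ACTivate-only loss, 0.84 SD is hard to tell apart from just over 0.8. This stands, so the table is illustrative. It does not supply the missing year-3 allowance.
3. **The planned model adjusts for age, gender and disease.** If those covariates explained about 12% of the variance they would offset 20% equal loss, and about 23% would offset 30% (1 − (0.824/0.876)² = 0.12; 1 − (0.824/0.940)² = 0.23). No such correlation is given, and the protocol's own figure reproduces without adjustment.
4. **Twenty may mean evaluable patients, with 24 recruited to secure them.** Then 20:32 gives 0.81 SD and 20:28 gives 0.84 SD, so the claim nearly survives 30% control loss. Section 6 attaches no time point to the four extra recruits, and Section 4 stops at 20 in total, so the text does not establish this reading.
5. **It is a small Stage IB pilot.** True, and no larger sample is asked for. The protocol nonetheless states a formal power and a difference in metres, and these should describe the analysis they accompany.

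**Conclusion.** The concern holds. The hypothesis and the model use year 3, the attrition allowance uses Day 90, and the described control comparison uses Day 30 and Day 90. The power arithmetic is correct for 10% loss, but nothing in the documents supports 10% as the total loss by year 3.

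The size of the shortfall cannot be fixed from the documents. Over an assumed 20 to 40% loss, the detectable difference is 0.88 to 1.02 SD with equal loss, or 0.84 to 0.94 SD if only ACTivate patients are lost. Power at 0.82 SD falls to 75–62% or 78–69% respectively. These figures rest on an unadjusted two-sided comparison at 1:2 allocation. The metre values also rest on the implied 19.5 m SD. The mismatch itself is certain, and it should be fixed.

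**What to change.** **If year 3 stays primary**, as H1 and the Section 11 model state:

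- In Section 11, replace the 90-day attrition clause with an assumed total loss by year 3 (death, drop-out and missed visit), given separately for ACTivate and controls. Add the evaluable numbers, the detectable difference in SD and the SD used to convert it to metres. For example, 30% loss in both groups leaves 14:28 and gives 80% power for 0.94 SD; 30% loss in ACTivate with 40 controls who have year-3 data leaves 14:40 and gives 0.89 SD.
- Say whether controls are selected for having a year-3 walk or are subject to loss like the treated group.
- In Sections 4 and 6, say whether the 24 recruits are meant to cover loss by year 3.
- In Section 4, Measures, name the year-3 control comparison as primary, with Day 30 and Day 90 as secondary.

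**If Day 90 was intended**, change H1 and the Section 11 model to Day 90 so that all the sections agree.

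**Cost.** Keeping year 3 needs text edits and a less favourable stated detectable difference. It adds no patients or visits, because the planned follow-up and routine evaluation already extend to year 3. Moving to Day 90 would change the primary endpoint, which is a substantive decision for the sponsor.
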